TSS_{50W24} rate is defined as the proportion of subjects who achieve at least 50% reduction in total symptom score at Week 24 from baseline. TSS scores obtained after confirmed disease progression or start of post-study treatment will not be included in the analysis. Subjects who do not have TSS score at Week 24 will be treated as non-responders. Subjects who do not receive any study drug will be treated as non-responders. TSS_{50W24} rate will be analyzed using the statistical method described for binary variables in Section 8.1.

TSS₅₀ rate any time is defined as the proportion of subjects who achieve at least 50% reduction in total symptom score from baseline at any time during the study. TSS scores obtained after confirmed disease progression or start of post-study treatment will not be

included in the analysis of TSS₅₀ rate. Subjects who do not have any TSS score after randomization will be treated as non-responders. Subjects who do not receive any study drug will be treated as non-responders. TSS₅₀ rate will be analyzed using the statistical method described for binary variables in Section 8.1.

Time to first TSS₅₀ is defined as the time from randomization to the first date of achieving TSS₅₀. Time to first TSS₅₀ will be summarized descriptively for each treatment arm.

Duration of TSS₅₀ is defined as the time from the first date of achieving TSS₅₀ to the first date of loss of TSS₅₀. Loss of TSS₅₀ is defined as not maintaining TSS₅₀ and at least 50% increase in TSS from nadir (the lowest score in the previous weeks). Subjects who do not lose TSS₅₀ response will be censored at the last TSS assessment. Subjects with ≥ 2 consecutive missing TSS scores prior to losing TSS₅₀ response will be censored at the last non-missing TSS assessment prior to losing TSS₅₀ response. The distribution of duration of TSS₅₀ will be estimated for each treatment arm using Kaplan-Meier methodology. Median duration of TSS₅₀ and the corresponding 95% confidence interval will be provided for each treatment arm. Only subjects who achieve TSS₅₀ at any time will be included in the analysis of duration of TSS₅₀.

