TSS response rate at any time during the study is defined as proportion of subjects who achieved change in TSS score from baseline \leq MCT at any time during the study. The MCT, derived using anchor-based analyses, has been determined to be at least 10 points for improvement in TSS from baseline. The validation of MCT of -10 is described in the Psychometric Analysis Report. TSS scores obtained after confirmed disease progression or start of post-study treatment will not be included in the analysis of TSS response rate. Subjects who do not have any TSS score after randomization will be treated as non-responders. Subjects who do not receive any study drug will be treated as non-responders. TSS response rate will be analyzed using the statistical method described for binary variables in Section 8.1. Similar analyses will be performed for TSS response rate at Week 24. The maximum reduction in TSS from baseline at any time will be summarized.

Time to TSS response is defined as the time from randomization to the first date of achieving TSS response based on MCT of at least 10 points. Time to first TSS response will be summarized descriptively for each treatment arm.

Duration of TSS response is defined as the time from the first date of achieving TSS response to the first date of loss of TSS response. Loss of TSS response is defined as diminishment of TSS below MCT improvement of 10 points. Subjects who do not lose TSS response will be censored at the last TSS assessment. Subjects with ≥ 2 consecutive missing TSS scores prior to losing TSS response will be censored at the last non-missing TSS assessment prior to losing TSS response. The distribution of duration of TSS response will be estimated for each treatment arm using Kaplan-Meier methodology. Median duration of TSS response and the corresponding 95% confidence interval will be provided for each treatment arm. Only subjects who achieve TSS response at any time will be included in the analysis of duration of TSS response. Sensitivity analysis of duration of TSS response may be performed by accounting for disease progression or death.

In addition, descriptive summaries of weekly TSS scores and individual symptom scores, change from baseline and percent change from baseline will be provided for each treatment arm. Change and percent change in TSS scores and individual symptom scores from baseline at Week 24 may also be presented graphically for each treatment arm.

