8.4.1.9 Duration of SVR₃₅

Duration of SVR₃₅ is defined as the time from the first date of SVR₃₅ to the first assessment where SVR₃₅ is not maintained and the spleen volume is $\geq 25\%$ increase from nadir (the lowest spleen volume in the previous assessments), confirmed relapse or leukemic transformation per IWG criteria, whichever is earlier. Subjects without the

defined events will be censored at the date of the last spleen volume assessment, the last disease assessment, the last bone marrow assessment, or the last hematology lab test, whichever occurs the latest and on or prior to the start of the post-study treatment.

The distribution of duration of SVR₃₅ will be estimated for each treatment arm using Kaplan-Meier methodology. Median duration of SVR₃₅ and the corresponding 95% confidence interval will be provided for each treatment arm. There will be no statistical comparison for duration of SVR₃₅.

Only subjects who achieve SVR₃₅ will be included in the analysis.

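### The durations of TSS50 and TSS response have no stop at confirmed progression, although the matching response rates do

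*SAP*

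**What the plan says.** All of the following is in SAP 8.4.1.1 unless another section is named.

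- **Rates.** For the threshold-based (MCT, 10-point) response, "TSS scores obtained after confirmed disease progression or start of post-study treatment will not be included in the analysis of TSS response rate". The any-time TSS50 rate has the same exclusion, again worded for the rate: such scores are not "included in the analysis of TSS₅₀ rate". The Week 24 TSS50 rate excludes them too.
- **Durations.** Both end only at a loss defined by the score. For the threshold-based response, "Loss of TSS response is defined as diminishment of TSS below MCT improvement of 10 points". For TSS50, loss means that the 50% reduction is not maintained and the score has risen at least 50% from nadir. Without a loss, the rules are "Subjects who do not lose TSS response will be censored at the last TSS assessment" and "Subjects who do not lose TSS₅₀ response will be censored at the last TSS assessment". The only other censoring rule concerns two or more consecutive missing scores. Progression, post-study treatment and death appear in neither main definition.
- **Sensitivity analysis.** One that accounts for progression or death is optional. It is named only for the threshold-based duration and does not mention post-study treatment.
- **Duration of SVR35 (SAP 8.4.1.9).** Confirmed relapse and leukemic transformation end the response. The censoring date is the last of several assessments, "whichever occurs the latest and on or prior to the start of the post-study treatment".

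**The concern.** One response has two follow-up limits. A score recorded after confirmed progression cannot make a subject a responder, yet it can lengthen that subject's response. The Kaplan-Meier duration then mixes durability of the response up to treatment failure with symptom control after it, and it cannot be read beside the rate, or beside duration of SVR35, on equal terms.

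Duration of disease response, including TSS, is part of the first secondary objective (protocol section 3, SAP 2.1), and these two summaries are its direct measure for symptoms. At stake is how they are interpreted, not a hypothesis test.

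**Working it through.** **Step 1. Does a general rule close the gap?** SAP 8.1 defines confirmed progression but sets no default cut-off for scores. SAP 8.2 sends time-to-event censoring back to the endpoint sections. The definitions in 8.4.1.1 therefore stand as written.

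| Analysis | Scores after confirmed progression | Scores after post-study treatment | Progression as event |
|---|---|---|---|
| TSS50 and TSS response rates | excluded | excluded | not applicable |
| Duration of TSS50 | no limit stated | no limit stated | no |
| Duration of TSS response | no limit stated | no limit stated | no (optional sensitivity analysis only) |
| Duration of SVR35 | no limit stated | censoring date limited | relapse and leukemic transformation only |

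**Step 2. Which scores are affected?** Protocol 5.5 allows study treatment to continue after progression or relapse, with monitoring per Appendix D. Appendix D schedules MFSAF daily through the end of Week 36, so post-progression scores are planned data for these subjects. Protocol 5.7 moves subjects who start another treatment to survival follow-up, and Appendix D shows no MFSAF there. Scores after post-study treatment should therefore be few.

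**Step 3. How much time can be added for one subject?** IWG assessments in this period are at Week 13 Day 1 (day 12 × 7 + 1 = 85) and Week 25 Day 1 (day 24 × 7 + 1 = 169). The last day of Week 36 is day 36 × 7 = 252. On schedule, the post-progression time that can be added is at most 252 − 85 = 167 days (about 24 weeks) for progression first seen at Week 13, or 252 − 169 = 83 days (about 12 weeks) for Week 25. Progression found at an unscheduled assessment could change these limits.

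**Step 4. What does this do to the estimate?** The documents give no figure for these durations, so there is none to reproduce and every input here is assumed:

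- 55 responders;
- 60% still in response at 24 weeks by score alone, with a constant hazard of loss that is the same after failure;
- a share f of responders per 24 weeks reaching confirmed progression or new therapy, with f = 5%, 10% or 20%;
- half of those failures being progression.

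Score-only rule: S(20) = 0.60^(20/24) = 65.3%.

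Proposed rule (progression is an event, new therapy is independent censoring): S(20) = 0.60^(20/24) × (1 − f)^(0.5 × 20/24).

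| f per 24 weeks | Calculation | Proposed rule | Fall from 65.3% |
|---|---|---|---|
| 5% | 0.653 × 0.979 | 63.9% | 1.4 points |
| 10% | 0.653 × 0.957 | 62.5% | 2.8 points |
| 20% | 0.653 × 0.911 | 59.5% | 5.8 points |

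The standard error with 55 responders is √(0.653 × 0.347 / 55) = 6.4 points at 65.3% and √(0.595 × 0.405 / 55) = 6.6 points at 59.5%, so about 6.5. The falls are about 0.2, 0.4 and 0.9 of a standard error.

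If every failure were instead censored, independent censoring would leave the estimate at 65.3%. The shift comes entirely from counting progression as an event.

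**The case against.** The best defence is that duration of a symptom response, ended only by symptom scores, is a coherent quantity. Counting progression as its end is partly a choice of estimand. The comparison with SVR35 is imperfect as well: SAP 8.4.1.9 counts confirmed relapse and leukemic transformation rather than all confirmed progression, and protocol 7.3 defines that duration by volume alone. The SAP also shows awareness of the issue through its optional sensitivity analysis.

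This stands as a reason to report both versions. It does not explain why the same scores are barred from the rate and admitted to the duration, and the optional analysis leaves out duration of TSS50 and post-study treatment.

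A reader might infer three stronger things that the documents do not support:

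- *That an arm with more new therapy will look more durable.* Subjects who start another treatment have no scheduled MFSAF, so little score data exists to produce that effect.
- *That the effect could reach two standard errors.* At f = 20% that requires every failure, new therapy included, to count as an event: 0.653 × 0.80^(20/24) = 54%, a fall of about 11 points. Nothing in the documents supports that failure rate, and a rule that censors at new therapy does not give that result.
- *That the bias always favours longer durations.* Losses of response after progression also count as events under the present rule. Compared with censoring at progression, the present rule could give shorter durations if symptoms worsen afterwards.

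**Conclusion.** The mismatch is real for both durations, and no other SAP rule repairs it. In practice it concerns subjects kept on study drug after confirmed progression who still hold a symptom response, up to Week 36. On the stated assumptions it moves the 20-week estimate by about 1 to 6 points, which is within one standard error. The result depends on the assumed failure rate, the half-and-half split and an unchanged loss hazard after failure. The 20-week estimate is only an illustration, since the SAP names the median as its summary.

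A reader might also infer a threat to the trial's tested results. There is none: protocol 3.3 lists both durations as exploratory, SAP 8.4.1.1 treats them as supplementary and summarises them per arm, and neither is in SAP Table 1. This is a minor point, worth correcting because the change is small and the durations will be read beside the rates.

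**What to change.** In SAP 8.4.1.1, for both duration of TSS50 and duration of TSS response:

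1. Use only TSS scores on or before confirmed progression or the start of post-study treatment, as the rates do.
2. Count confirmed progression as the end of response.
3. Censor at the last TSS score before post-study treatment.
4. State how death is handled.
5. Report the present score-only version alongside as a committed sensitivity analysis for both durations, replacing the optional one that covers only the threshold-based duration.

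The cost is about two sentences in the SAP, a small programming change and one extra Kaplan-Meier analysis. The stated durations may be slightly shorter. No sample size, alpha or data collection changes.

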APPENDIX D. ACTIVITY SCHEDULE

The following table shows the required activities. The individual activities are described in detail in the **Operations Manual**.

Study Activities Table

Activity	Screening/ Baseline	Week 1	Week 1	Week 2	Week 3	Week 5	Week 7	Week 9	Week 13, 17, 21, 25	Q12 weeks as of Week 37	Treatment Completion Visit	30-Day Safety Visit (± 3 Days)	Post-Treatment Visits (± 3 Weeks)	Survival Follow Up
	Day -28 to Day -1	Day 1	Day 2	Day 1 (± 1 day)	Week 13, 17, 21 Day 1 (± 2 days). Week 25 Day 1 (± 3 days)	From Week 37 Day 1 (± 4 days)								
INTERVIEWS & QUESTIONNAIRES														
Informed consent	✓													
Eligibility criteria	✓													
Medical/surgical/transfusion history	✓	✓												
Alcohol and nicotine use	✓													
Adverse event assessment	✓	✓	✓	✓	✓	✓	✓	✓	✓	✓	✓	✓		
Prior/concomitant therapy/transfusion	✓	✓	✓	✓	✓	✓	✓	✓	✓	✓	✓			
Post-treatment therapy/transfusion/surgery												✓	✓	✓
MFSAF v4.0 (Daily)	✓	✓ (Daily through end of Week 36)												
EORTC QLQ-C30 v3.0		✓				✓			✓ (Week 13, 25)	✓	✓			
PROMIS Fatigue SF 7a	✓	✓				✓			✓ (Week 13, 25)	✓	✓			
EQ-5D-5L		✓				✓			✓ (Week 13, 25)	✓	✓			
PGIC									✓ (Week 13, 25)					

Activity	Screening/ Baseline	Week 1	Week 1	Week 2	Week 3	Week 5	Week 7	Week 9	Week 13, 17, 21, 25	Q12 weeks as of Week 37	Treatment Completion Visit	30-Day Safety Visit (± 3 Days)	Post-Treatment Visits (± 3 Weeks)	Survival Follow Up
	Day -28 to Day -1	Day 1	Day 2	Day 1 (± 1 day)	Week 13, 17, 21 Day 1 (± 2 days). Week 25 Day 1 (± 3 days)	From Week 37 Day 1 (± 4 days)								
PGIS	✓	✓							✓ (Week 13, 25)					
ECOG performance status	✓	✓		✓	✓	✓	✓	✓	✓	✓	✓			
Survival follow-up call (approximately every 2 months for up to 8 years)														✓
LOCAL LABS & EXAMS														
MRI (or CT scan) for spleen assessment	✓								✓ (Week 13, 25)	✓ (Week 37, 49, 73, 97)	✓		✓	
12-lead ECG	✓					✓					✓			
Vital signs: including height (Screening only), weight, BP, pulse, and body temperature	✓	✓		✓	✓	✓	✓	✓	✓	✓	✓	✓		
Physical examination including skin examination, spleen and liver measurement by palpation	✓	✓		✓	✓	✓	✓	✓	✓	✓	✓		✓	
Disease Assessment by IWG									✓ (Week 13, 25)	✓ (Week 37, 49, 73, 97)	✓		✓	
Serum/urine pregnancy test	✓	✓				✓		✓	✓ (monthly from Week 25 where a	✓ (monthly where a regulatory requirement)	✓			

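### The missing-score rule for the two TSS duration analyses does not say that the gap must come directly before the loss; read literally, it discards directly observed losses and lengthens the Kaplan-Meier durations

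*SAP*

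**What the plan says.** SAP 8.4.1.1 defines both durations from the first date of response to the first date of loss. For the MCT-based response, "Loss of TSS response is defined as diminishment of TSS below MCT improvement of 10 points"; no confirmation is required. For TSS50, loss means that TSS50 is no longer maintained and that there is "at least 50% increase in TSS from nadir (the lowest score in the previous weeks").

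The gap rule for TSS response covers subjects with two or more consecutive "missing TSS scores prior to losing TSS response will be censored at the last non-missing TSS assessment prior to losing TSS response". The TSS50 paragraph has the same rule: such a subject "will be censored at the last non-missing TSS assessment prior to losing" the response. In both definitions, subjects who never lose response are censored at their last TSS assessment, whether or not they had a gap.

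The score interval appears to be weekly, since the section plans "descriptive summaries of weekly TSS scores and individual symptom scores", but part of the scoring text is redacted. Protocol Appendix D schedules the diary as "Daily through end of Week 36".

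**The concern.** Two features of the wording combine badly. The gap may lie anywhere before the loss, and the censoring date is the last score before the loss. If scores resume after a gap, that last score is the in-response score just before the failure.

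A subject with an early gap who keeps responding stays at risk to the last assessment. The same subject who loses response is removed at the moment of loss. After a gap, a responder therefore adds time at risk but cannot add an event. That is censoring triggered by the outcome, and it raises the Kaplan-Meier curve even when gaps occur at random.

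At stake are the per-arm median durations of symptom response, which would be reported side by side. Programmers who read the sentence differently would also report different medians from the same data.

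**Working it through.** **1. Two worked cases.** First response is at Week 6 and loss is observed at Week 20 in both.

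| Missing weeks | Literal reading | Gap directly before loss only |
|---|---|---|
| 9-10, in response at 11-19 | Censored at Week 19 (19 − 6 = 13 weeks) | Event at Week 20 (20 − 6 = 14 weeks) |
| 18-19 | Censored at Week 17 (17 − 6 = 11 weeks) | Censored at Week 17 (11 weeks) |

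The readings part only when scores resume in response before the loss.

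**2. Does anything else in the SAP settle it?** Section 8.2 works from observed data and censors only subjects without the event, but it applies unless otherwise specified, and 8.4.1.1 specifies otherwise. Duration of SVR35 (8.4.1.9) has no gap rule. The one sensitivity analysis named for duration of TSS response is optional and concerns progression or death.

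**3. Why random gaps still bias the curve.** The SAP gives no figure for these durations, so there is none to reproduce. Assume weekly scores that are missing independently with probability m. Let a be the probability of no run of two so far with the latest score present, and b the same with the latest score missing. Each week, a becomes (a + b)(1 − m) and b becomes a·m. The chance of at least one run of two or more is 1 − a − b:

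| m | Within 12 weeks | Within 24 weeks |
|---|---|---|
| 5% | 2.6% | 5.4% |
| 10% | 9.7% | 19.2% |
| 20% | 32.2% | 55.4% |

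Under the literal rule, the estimated weekly hazard is roughly the true hazard times (1 − share with a gap). With a true hazard of 0.04 and m = 10%, it is about 0.04 × (1 − 0.097) = 0.036 at 12 weeks and 0.04 × (1 − 0.192) = 0.032 at 24 weeks.

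**4. Simulation with two-week gaps.** Assumptions: 40,000 responders per scenario, constant weekly loss hazard, follow-up of 12 to 32 weeks after first response (first response at Week 24 to Week 4 with a diary ending at Week 36), and two-week gaps starting at random and unrelated to outcome. The true median is 16 to 17 weeks on the weekly grid.

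| Gap starts per week | Observed losses removed, literal | Median, literal | Median, narrow rule |
|---|---|---|---|
| 1% | about 9% | about 18 | 17 |
| 2% | about 17% | about 20 | 17 |
| 4% | about 30% | about 26 | 18 |

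The last literal median varies from 26 to 28 between runs. The narrow rule removes about 2.5% to 10% of observed losses. With true medians of 4 or 8 weeks, the literal and narrow medians differ by 0 to 1 week at all three gap rates.

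**5. Second model.** 100,000 responders, 28 weeks of follow-up, and missingness either independent or clustered (probability 0.5 of missing a week if the previous week was missing). The true median is ln(0.5)/ln(1 − hazard): 17.0 weeks at hazard 0.04 and 11.2 at 0.06 (12 on the weekly grid).

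| Hazard | Pattern | Literal median at 5%, 10%, 20% missing | Losses removed, literal |
|---|---|---|---|
| 0.04 | independent | 18, 19, 27 | 2.8%, 10.1%, 31.6% |
| 0.04 | clustered | 20, 23, not reached | 13.9%, 25.9%, 45.7% |
| 0.06 | independent | 12, 12, 15 | 2.5%, 9.2%, 29.1% |
| 0.06 | clustered | 13, 14, 19 | 12.5%, 23.7%, 42.0% |

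The literal-rule curve lay above the true curve at 12 and 24 weeks in every scenario. At hazard 0.04 with clustered 10% missingness, the 24-week estimate was 0.487 under the literal rule, 0.407 under the narrow rule and 0.377 when the first observed loss counts as the event, against a true 0.374.

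**The case against.** The best defence is that the sentence is a loosely worded form of the usual missed-assessment rule, which covers a gap directly before the event. On that reading, the last non-missing score before the loss is also the last score before the gap, so both halves of the sentence fit. In the Week 9-10 case, by contrast, the word non-missing does no work. This stands as a plausible account of intent, and it means that a reader should not infer that a biased analysis was deliberately chosen. It does not cure the text, which sets no such limit.

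A reader might also infer that a secondary result is at risk, because the secondary objectives mention duration of disease response including TSS. The documents do not support that. The duration endpoint listed as secondary is duration of SVR35. Both TSS durations are exploratory in Protocol 3.3, other endpoints in SAP 3.3, supplementary in SAP 8.4.1.1, and absent from SAP Table 1. Only per-arm Kaplan-Meier summaries are described, with no between-arm test.

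Nor do the documents support the inference that the more toxic arm would look more durable. That requires diary gaps to differ by arm; no missingness rates are given, and the simulations do not model a difference.

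Finally, the redaction hides how many daily scores make a valid weekly score, so how often the rule would fire cannot be known from the public text.

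**Conclusion.** The concern holds as a drafting defect with a known direction and an undetermined size. Applied as written, the rule removes directly observed losses and biases both durations upward, without any link between gaps and outcome. The bias is negligible to modest if gaps are rare or responses short: at hazard 0.06, the median is unchanged at 5% and 10% independent missingness. It is large if gaps are frequent or clustered and responses last around 16 weeks or more. All of this rests on assumed loss hazards and gap rates and on a weekly interval inferred from the visible text. Under the narrow reading the bias is small at most of the rates examined, although it reaches 21 weeks against a true 17 at 20% clustered missingness. No primary or ranked result and no alpha is affected. Severity: minor.

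**What to change.** In both definitions, replace the gap sentence with text to this effect: a subject is censored only when loss of response is first observed immediately after two or more consecutive missing weekly scores, and then at the last non-missing score before that gap; a gap followed by a score still in response is ignored, and a later loss counts as an event.

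Add a sensitivity analysis that counts every observed loss as an event, since even the narrow rule drops some losses.

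The cost is two sentences and one extra Kaplan-Meier run per duration, with no new data and no effect on alpha or trial conduct. Reported durations may be somewhat shorter. If the narrow rule was always intended, the edit only records it.
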